#### **Extended Safety Follow-up Phase:**

Patients who discontinue avelumab therapy for any reason at any point in the study will be entered into an extended safety follow-up period of 90 days. Treatment will then be at the investigator or local oncologist's discretion. All subjects will be observed for the possible occurrence of delayed irAE's. Survival data and information about subsequent therapies will be collected. Tissue samples in patients undergoing second surgical resections will be obtained for further biomarker analysis.

**Number of Subjects:** 30 patients

**Target population:** patients with newly diagnosed GBM who will be undergoing standard temozolomide/radiotherapy followed by 6 cycles of temozolomide.

#### **Inclusion criteria:**

1. Signed informed consent
2. Age  $\geq$  18 years
3. Present with newly diagnosed supratentorial Glioblastoma (GBM) with a tissue diagnosis that has been established following either a surgical resection or biopsy. This includes treatment-naïve (chemotherapy and radiotherapy)- patients with prior diagnosis of a lower grade astrocytoma that has been upgraded to a histologically verified GBM
4. Karnofsky performance score of 70 or higher
5. Patients entering the study must be on a stable dose of no more than 12 mg (maximum) of Dexamethasone (or equivalent) daily for symptoms related to cerebral edema.
6. Will be or is undergoing or has received the standard therapy of chemo radiation therapy (60Gy in 30 fractions of 2Gy/day with concurrent temozolomide of 75mg/m^2 per day PO or as per local practise) no more than 21 days ago
7. Has not yet begun but will begin standard monthly temozolomide therapy
8. Patient must have at least 1 formalin fixed paraffin embedded tumor tissue block representative of glioblastoma available for biomarker analysis and determination of MGMT status (if not already done). If tumor block is not available or not of adequate quality, sufficient pathology material, representative of glioblastoma, must be available

9. Adequate hematological function defined by absolute neutrophil count (ANC)  $\geq 1.5 \times 10^9/L$ , platelet count  $\geq 100 \times 10^9/L$ , and hemoglobin  $\geq 9 \text{ g/dL}$  (may have been transfused)
10. Adequate hepatic function defined by a total bilirubin level  $\leq 1.5 \times$  the upper limit of normal (ULN) range and AST and ALT levels  $\leq 2.5 \times$  ULN for all subjects
11. Adequate renal function defined by an estimated creatinine clearance  $\geq 30 \text{ mL/min}$  according to the Cockcroft-Gault formula (or local institutional standard method)
12. Negative serum pregnancy test at screening for women of childbearing potential
13. Highly effective contraception for both male and female subjects if the risk of conception exists. (Note: The effects of the trial drug on the developing human fetus are unknown; thus, women of childbearing potential and men able to father a child must agree to use 2 highly effective contraception, defined as methods with a failure rate of less than 1 % per year. Highly effective contraception is required at least 28 days prior, throughout and for at least 30 days after avelumab treatment.)
14. International normalized ratio (INR) or PT (secs) and activated partial thromboplastin time (aPTT):
  - in the absence of therapeutic intent to anticoagulate the subject: INR  $\leq 1.5$  or PT  $\leq 1.5 \times$  ULN and aPTT  $\leq 1.5 \times$  ULN
  - in the presence of therapeutic intent to anticoagulate the subject: INR or PT and aPTT within therapeutic limits (according to the medical standard in the institution)

NOTE: Use of full-dose anticoagulants is permitted as long as the INR or aPTT is within therapeutic limits (according to the medical standard in the institution) and the patient has been on a stable dose of anticoagulants for at least two weeks prior to baseline visit.
15. Willing and able to comply with the protocol as judged by the Investigator

#### **Exclusion Criteria:**

1. Patients who have evidence of leptomeningeal disease,
2. Known significant pulmonary, cardiovascular, hepatic disorders or any other disease that in the opinion of the investigator would be contraindicated to receive anti PD-L1 therapy such as avelumab,
3. "Clinically significant (i.e., active) cardiovascular disease: cerebral vascular accident/stroke (< 6 months prior to enrollment), myocardial infarction (< 6 months prior to enrollment), unstable angina, congestive heart failure ( $\geq$  New York Heart Association Classification Class II), or serious cardiac arrhythmia requiring medication."
4. Prior treatment with bevacizumab or any checkpoint immune blockade therapies
5. Any other concomitant immunosuppressant other than temozolomide and steroids or any recent (within 3 months) experimental therapy,
6. Patients who have finished their radiotherapy course more than 3 weeks prior to baseline,
7. Prior organ transplantation, including allogeneic stem-cell transplantation
8. Significant acute or chronic infections including, among others:

- Known history of testing positive test for human immunodeficiency virus (HIV) or known acquired immunodeficiency syndrome (AIDS),
- Positive test for HBV surface antigen and / or confirmatory HCV RNA (if anti-HCV antibody tested positive),

9. Active autoimmune disease requiring ongoing immunosuppressant therapy that might deteriorate when receiving an immunostimulatory agent:

- Subjects with diabetes type I, vitiligo, psoriasis, hypo or hyperthyroid disease or any other autoimmune disease not requiring immunosuppressive treatment are at the investigator's discretion eligible
- Subjects requiring hormone replacement with corticosteroids are eligible if the steroids are administered only for the purpose of hormonal replacement and at doses  $\leq$  10 mg or 10 mg equivalent prednisone per day
- Administration of steroids through a route known to result in a minimal systemic exposure (topical, intranasal, intro-ocular, or inhalation) are acceptable

10. Known severe hypersensitivity reactions to monoclonal antibodies (Grade  $\geq$  3 NCI-CTCAE v 4.03), any history of anaphylaxis, or uncontrolled asthma (that is, 3 or more features of partially controlled asthma),

11. Pregnancy or lactation,

12. Known alcohol or drug abuse,

13. Any psychiatric or cognitive condition that would prohibit the understanding or rendering of informed consent,

14. Vaccination within 4 weeks of the first dose of avelumab and while on trial is prohibited except for administration of inactivated vaccines.

15. Any other malignancy within 5 years prior to baseline, except for adequately controlled limited basal cell carcinoma of the skin, squamous carcinoma of the skin or carcinoma in situ of the cervix

16. Evidence of any active infection requiring hospitalization or IV antibiotics within 2 weeks prior to baseline

17. Persisting toxicity related to prior therapy (NCI CTCAE v. 4.03 Grade  $>$  1); however, alopecia, sensory neuropathy Grade  $\leq$  2, or other Grade  $\leq$  2 not constituting a safety risk based on investigator's judgment are acceptable.

18. Other severe acute or chronic medical conditions including colitis, inflammatory bowel disease, pneumonitis, pulmonary fibrosis or psychiatric conditions including recent (within the past year) or active suicidal ideation or behavior; or laboratory abnormalities that may increase the risk associated with study participation or study treatment administration or may interfere with the interpretation of study results and, in the judgment of the investigator, would make the patient inappropriate for entry into this study.

**Investigational Product: Dose/Route/Regimen:**

The active pharmaceutical ingredient in avelumab drug product is a fully human antibody (calculated molecular weight of 143832 Dalton) of the immunoglobulin G (IgG) 1 isotype that specifically targets and blocks PD-L1, the ligand for PD-1.

Avelumab drug product is a sterile, clear, and colorless concentrate for solution intended for intravenous (IV) infusion. The drug is presented at a concentration of 20 mg/mL in single-use glass vial containing 200 mg of avelumab.

Avelumab drug product must be stored at 2°C to 8°C until use, and it must not be frozen. Rough shaking of avelumab product must be avoided. Avelumab drug product must be diluted with 0.9% saline solution; alternatively, a 0.45% saline solution can be used if needed. It is recommended that the diluted avelumab solution is used immediately. Avelumab is administered as a 1-hour IV infusion at a dose of 10mg/kg IV Q2weeks.

**Premedication:** In order to mitigate infusion related reactions, a premedication with an antihistamine and with paracetamol (acetaminophen) 30 to 60 minutes prior to the first 4 infusion of avelumab is mandatory (for example, 25-50 mg diphenhydramine and 500-1000 mg paracetamol IV or oral). *Premedication should be administered for subsequent avelumab infusions based upon clinical judgment and presence/severity of prior infusion reactions. This may be modified based on local treatment standards and guidelines, as appropriate.*

**Setting:** Avelumab should be administered in a setting that allows for immediate access to an emergency care unit or equivalent environment and administration of therapy for anaphylaxis, such as the ability to implement immediate resuscitation measures. Steroids (dexamethasone 10 mg), epinephrine (1:1,000 dilution), allergy medications (IV antihistamines), bronchodilators, or equivalents, and oxygen should be available for immediate access.

**Observation period:** Following avelumab infusions, patients must be observed for 2 hours post infusion for potential infusion related reactions. The observation period will be reduced to 30 minutes after the 4th infusion.

### **Safety Assessments:**

Safety assessments will consist of monitoring and recording protocol-defined adverse events (AEs) and serious adverse events (SAEs), measurement of protocol-specified haematology, chemistry, and urine analysis variables; measurement of protocol specified vital signs; clinical assessments and other protocol-specified tests that are deemed critical to the safety evaluation of the study drug.

Only clinically significant laboratory abnormalities that require active management (i.e. those that require study drug dose modification, discontinuation of study treatment, more frequent follow-up assessments, further diagnostic investigation, etc.) will be recorded as AEs or SAEs.

All assessments will be scheduled as indicated in the schedule of assessment tables. Additional assessments may be performed as clinically indicated. Adverse events will be graded according to NCI-CTC AE, version 5.0.

## **Routine laboratory assessments:**

Laboratory tests including haematology, blood chemistry and urine analysis will be performed at screening and baseline and then Q2weeks prior to each avelumab dose and at the end of treatment visit and at 30 days post-treatment in the extended safety follow-up phase.

Urine pregnancy test for women of childbearing potential must be performed at baseline and least every month during treatment.

Free T4 and TSH must be performed at baseline and at least every 8 weeks during treatment and at end of treatment or 30 days post-treatment safety follow-up (if not performed in the previous 8 weeks).

### **Hematology**

Haemoglobin, platelet count, WBC count, absolute neutrophils and lymphocytes counts

### **Coagulation (at screening and baseline only)**

INR or PT (secs), and aPTT

### **Blood Chemistry**

Including total bilirubin, AST, ALT, LDH, GGT, alkaline phosphatase, albumin, serum creatinine, and electrolytes (sodium, potassium, calcium), amylase, lipase, glucose, ck, phosphate

### **Endocrinology**

Free T4 and TSH must be performed at baseline and at least every 8 weeks during treatment

### **Urinalysis**

Routine urine analysis by dipstick

### **Clinical assessments**

A general physical and neurological exams will be performed at screening, baseline and then monthly during the first 3 months of the study then Q3months and at the end of avelumab treatment and 30 days after the last treatment.

Vital signs will be done at screening, baseline and before and during each infusion of avelumab

Pre-infusion questionnaire will be administered by the infusion nurse prior to every infusion of avelumab

### **Radiological assessment**

MRI or CT scan will be performed as per local standard of care (ie Q3-4 months).

Study specified gadolinium enhanced MRI or CT scan for efficacy measures of the brain will be done at baseline and Q52weeks or in case of premature withdrawal at end of study visit at the investigator' discretion.

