***At week 260 or end of study visit***

**Progression of Disease (PD)** will be defined as a  $\geq 25\%$  increase on the 12 month MRI in the sum of the product of the biperpendicular diameters of enhancing disease; or new lesions; or substantial worsened T2/FLAIR; or significant clinical neurological decline unexplained by a change in medication or concurrent comorbidities. The SPD is the sum of the products of biperpendicular diameters of the measurable enhancing lesions (max 5 lesions)

**Complete Response (CR)** will be defined as the disappearance on the month 12 MRI or CT scan of all enhancing disease, no new lesions, with stable or improved T2/FLAIR; no more than physiological steroids; clinically stable or improved

**Partial Response (PR)** will be defined as a  $\geq 50\%$  decrease on the month 12 MRI or CT scan in the sum of the products of the biperpendicular diameters of enhancing disease, no new lesions, stable or improved T2/FLAIR, stable ( $>2$  months) or decreased steroid dose, clinically stable or improved

**Stable Disease (SD)** will be defined as a patient who do not qualify for complete response, partial response, or progressive disease, stable or improved T2/FLAIR; stable ( $>2$  months) or decreased steroid dose, clinically stable or improved

**Overall survival (OS)** will be defined as the time from baseline to the date of death from any cause. Follow up times of patients who are lost to follow up will be recorded and censored. The censoring time point (date last known to be alive) will be recorded.

**Objective Response Rate (ORR)** will be defined as the number of patients with CR + PR - divided by the total number of patients at time points 12, and every 12 months thereafter.

**Progression Free Survival (PFS)** will be defined as the time from baseline to documented PD or death from any cause. Patients without event would be censored at the last valid tumor assessment (before starting new anti-cancer therapy) at which they were known to be progression-free.

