### **9.3.5. Disease assessment Evaluation**

Disease assessment evaluations will be based according to the immunotherapy Response Assessment for Neuro-Oncology (iRANO).

Study specified MRI's or CT scan will be done at the baseline, week 52 and every 52 weeks. These will be performed at a single MRI center using a predefined acquisition protocol (appendix 3). Change in the corticosteroid dose within the 2 week period preceding the week 52 MRI or CT scan will be discouraged.

All other MRI's or CT scan performed mainly for safety reasons will be done locally according to standard practise usually every 3 to 4 months. Copies of these MRI's or CT scan will be obtained for review by the investigator. These will also be used after the 6 month mark to ascertain if there is radiological evidence of progression according to the iRANO criteria (see page 29).

It is strongly encouraged that for a given patient the same physician will do the physical and neurological evaluations to confirm AE's or tumor progression during the entire study

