### **12.3.2. Secondary Endpoints**

Based on the results of Stupp *et al* (2005) (3), if avelumab had no effect then we would expect to see one-year overall survival and progression-free survival rates of 60% and 27%, respectively. We will conclude that we have preliminary evidence of benefit if either of our observed rates is significantly better based on a one-sided t-test at the 0.2 level of significance. With our projected sample of 30, this corresponds to concluding benefit if at least 21 patients survive to one-year or if at least 11 have survived without progression of disease.

Radiological tumor response will be graded according to the immunotherapy Response Assessment for Neuro-Oncology (iRANO)

**Progression of Disease (PD)** will be defined as a  $\geq 25\%$  increase on the 12 month MRI or CT scan in the sum of the product of the biperpendicular diameters of enhancing disease; or new lesions; or substantial worsened T2/FLAIR; or significant clinical neurological decline unexplained by a change in medication or concurrent comorbidities. The SPD is the sum of the products of biperpendicular diameters of the measurable enhancing lesions (max 5 lesions).

**Complete Response (CR)** will be defined as the disappearance on the month 12 MRI or CT scan of all enhancing disease, no new lesions, with stable or improved T2/FLAIR; no more than physiological steroids; clinically stable or improved

**Partial Response (PR)** will be defined as a  $\geq 50\%$  decrease on the month 12 MRI or CT scan in the sum of the product of the biperpendicular diameters of enhancing disease, no new lesions, stable or improved T2/FLAIR, stable ( $>2$  months) or decreased steroid dose, clinically stable or improved

**Stable Disease (SD)** will be defined at 12 months when a patient do not qualify for complete response, partial response, or progressive disease, stable or improved T2/FLAIR; stable ( $>2$  months) or decreased steroid dose, clinically stable or improved

**Overall survival (OS)** will be defined as the time from baseline to the date of death from any cause.

**Objective Response Rate (ORR)** will be defined the number of patients with either CR or PR divided by the total number of patients.

**Progression Free Survival (PFS)** will be defined as the time from baseline to documented PD or death from any cause.

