### MRI Parameters

The MR imaging will be performed on a 1.5 T scanner (GE) in sagittal T1 SE, axial T2 TSE fatsat, axial FLAIR, and axial T1 TSE. After IV gadolinium injection, additional images will be obtained in axial T1 TSE and sagittal 3D T1 (FSPGR) with axial and coronal reconstructions. Details of the parameters are presented in tables below (table 4).

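### CT is allowed for the efficacy scans without condition, but CR, PR and SD each require a T2/FLAIR finding that CT does not give, and one of the four routes to progression is lost on CT

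*Protocol*

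**What the plan says.** **Modality.** In the synopsis under Radiological assessment, "Study specified gadolinium enhanced MRI or CT scan for efficacy measures of the brain will be done at baseline and Q52weeks". Section 9.3.5 agrees: "Study specified MRI's or CT scan will be done at the baseline, week 52 and every 52 weeks". The secondary endpoints (synopsis and 5.2) and the screening assessments (9.3.1.1) also allow either modality. No section says when CT may be used, asks for one modality per patient, or says how T2/FLAIR is scored on CT.

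**Acquisition.** Section 9.3.5 adds of the study scans: "These will be performed at a single MRI center using a predefined acquisition protocol (appendix 3". Appendix 3 is an MR specification: "The MR imaging will be performed on a 1.5 T scanner (GE) in sagittal T1 SE, axial T2 TSE fatsat, axial FLAIR, and axial T1". It contains no CT parameters.

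**Response.** In section 5.2, complete response is the "disappearance on the month 12 MRI or CT scan of all enhancing disease, no new lesions, with stable or improved T2/FLAIR". Partial response and stable disease carry the same T2/FLAIR condition. Section 12.3.2 and SAP 1.3.2 repeat all three definitions.

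**Progression.** This is a list of alternatives. After a 25% increase in enhancing area, section 12.3.2 continues "or new lesions; or substantial worsened T2/FLAIR; or significant clinical neurological decline unexplained by a change in medication or concurrent comorbidities". Section 5.2 ties the 25% increase to the 12-month MRI, whereas 12.3.2 and SAP 1.3.2 name MRI or CT.

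**Local scans.** Section 9.3.5 says of the locally obtained MRI or CT scans: "These will also be used after the 6 month mark to ascertain if there is radiological evidence of progression".

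**The concern.** T2 and FLAIR are MR sequences. Appendix 3 lists them as such, and CT does not produce them. Three of the four outcome categories therefore contain a condition that cannot be checked on a modality the plan permits. The complete response definition names CT and requires T2/FLAIR in the same sentence.

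Three things follow:

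- **ORR.** Whether a patient read on CT can count as a responder depends on an unwritten choice by the single study radiologist. A strict reading excludes the patient and lowers ORR.
- **PFS.** Losing the T2/FLAIR route can only remove or delay a progression. This works in the opposite direction to the ORR effect and leans towards progression-free status. Section 9.3.5 follows completely resected patients with no visible lesion for new lesions. They have no enhancing area to grow, so on CT a new lesion is the only imaging route left.
- **Size thresholds.** Section 9.3.5 compares the 12-month MRI or CT with baseline. A CT set against an MRI baseline adds a between-modality measurement difference at the 25% and 50% cut-offs.

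The one-year PFS count feeds a formal decision rule, so a one-directional reading error matters there.

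**Working it through.** **Step 1. What can be assigned on CT, as the definitions stand (5.2, 12.3.2, SAP 1.3.2).**

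| Category | Role of T2/FLAIR | Assignable on CT? |
|---|---|---|
| CR | required | no |
| PR | required | no |
| SD | required | no |
| PD | one of four alternatives | yes, by the other three |

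So 3 of 4 categories cannot be assigned on CT, and PD keeps 3 of its 4 routes: enhancing size, new lesions and clinical decline. A non-progressor read on CT has no category.

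**Step 2. The plan's own PFS rule.** Inputs from SAP 1.3.2: n = 30, no-effect one-year PFS 27%, one-sided level 0.2, benefit concluded if at least 11 are progression-free. With X binomial(30, 0.27):

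- P(X ≥ 10) = 0.276
- P(X ≥ 11) = 0.161

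Eleven is the smallest count with a tail probability of at most 0.2, so the rule is reproduced. The one-sample t-test that the plan names gives the same cut-off (p = 0.238 at 10, 0.144 at 11).

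**Step 3. Illustration of the PFS effect.** The documents give neither input, so both are assumptions:

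- c = share of patients read on CT
- t = share of one-year PFS events visible only on T2/FLAIR and picked up by nothing else by week 52

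Taking c and t as independent, the apparent no-effect PFS rate is 0.27 + 0.73 × c × t. The false-positive rate is P(X ≥ 11) at that rate.

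| c | t | c × t | Apparent rate | P(X ≥ 11) |
|---|---|---|---|---|
| 0 | any | 0 | 0.2700 | 0.161 |
| 10% | 5% | 0.005 | 0.2737 | 0.173 |
| 10% | 10% | 0.01 | 0.2773 | 0.185 |
| 10% | 20% | 0.02 | 0.2846 | 0.211 |
| 20% | 20% | 0.04 | 0.2992 | 0.266 |
| 30% | 30% | 0.09 | 0.3357 | 0.426 |

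The rate passes the nominal 0.20 at about c × t = 0.02. In patients, that is 30 × 0.73 × 0.02 = 0.44 expected to be wrongly counted as progression-free.

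**Step 4. ORR and size thresholds.** No figure can be derived. The documents give no CT share, no expected response rate and no between-modality measurement error.

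**The case against.** A reader might infer that every category, progression included, needs T2/FLAIR, so that a patient moved to CT cannot be classified at all and T2/FLAIR progression is always missed. The documents do not support this. Progression is an either-or list, and clinical progression under 5.2 needs no confirmatory imaging. Sections 8.2 and 8.4 add further triggers: bevacizumab or re-irradiation, and, after the first three months, dexamethasone for oedema beyond the stated dose or duration. PFS runs to documented progression or death and needs no CR, PR or SD label, so a CT patient still has a PFS value. Progression first visible on T2/FLAIR may be caught later by another route.

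It is also fair to say that MRI is plainly the intended modality: there is a single MRI centre, a detailed MR protocol and one study radiologist. That stands as evidence of intent, but it does not restrict CT. Section 9.3.5 allows CT and then places the scans under a protocol that a CT scan cannot follow. The two statements are unreconciled. The entry of no change that 9.3.5 provides, on MRI or CT, for completely resected patients without lesions covers only that group and is not one of the four categories.

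Finally, the size is unknown. One patient is 1/30 = 3.3 points, and the gap between 0.276 and 0.161 shows that one patient can decide the PFS conclusion. Both describe any single misclassification and neither measures the CT problem. If CT is rare, the effect is small. The study is mainly descriptive, and these are secondary endpoints.

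**Conclusion.** The point holds as an inconsistency in the secondary endpoint definitions. CT is permitted with no condition, while CR, PR and SD cannot be assigned on CT as written and one of four progression routes is unavailable there. This is more than missing detail, because the plan's own categories fail for a scan that the plan allows. The likely direction is a longer apparent PFS and, on a strict reading, a lower ORR.

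The size is conditional. On the assumed inputs, the PFS rule's false-positive rate stays below 0.20 when c × t is 0.01 and exceeds it from about 0.02. This rests on CT lacking T2/FLAIR (general imaging knowledge, consistent with Appendix 3) and on no other scan or clinical sign revealing the event by week 52. Overall survival and the primary safety endpoint are not touched. It should be corrected before the one-year analysis.

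**What to change.** Amend the synopsis, 5.2, 9.3.5, 12.3.2 and the SAP together:

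1. Efficacy scans are MRI under Appendix 3. CT is used for efficacy only when MRI cannot be done.
2. Follow-up uses the baseline modality where possible. If a patient has to switch, flag the scan and do not apply the 25% and 50% size thresholds across modalities without a stated rule.
3. On CT, record T2/FLAIR as not evaluable, grade response on the remaining criteria, and flag the patient.
4. Apply the same reading rule to local scans when they are used to determine progression (5.2 and 9.3.5). This governs how they count for the endpoint, not what is ordered locally.
5. Report the number of CT-assessed patients. Repeat one-year PFS counting CT-assessed non-progressors as progressed, and ORR counting them as non-responders. Both keep n = 30, so the rule of at least 11 of 30 still applies. Dropping these patients would leave the rule without its denominator.
6. Reconcile the 12-month modality in the progression definition: MRI in 5.2, MRI or CT in 12.3.2 and SAP 1.3.2.

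The cost is mostly wording, since MRI already has a full protocol. There is a little extra analysis, and a few patients who cannot have MRI are handled separately.
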